Approximately 166 subjects will be enrolled in the study. Since this is a supportive study to understand one of the possible mechanisms for IPTp effect, it is not powered for formal hypothesis testing. The sample size will yield a half width of a 2-sided 95% confidence interval (CI) to be ≤ 5 percentage points with probability=0.80 for the primary efficacy endpoint, using a large sample normal approximation to the binomial, provided the true underlying incidence is $\geq 95\%$, and assuming approximately 10% will drop out.

Independent Data Monitoring Committee (IDMC)

The IDMC constituted for IPTp will review safety data at regular intervals to be determined at the time of DMC charter development.

Study Schematic

090177e1811d3ccb\Approved\Approved On: 19-Feb-2010 20:59

SCHEDULE OF ACTIVITIES

Protocol Activity	Treatment			Follow Up Visits						
	Day 0 ^a	Day 1	Day 2	Day 7	Day 14	Day 21	Day 28	Day 35	Day 42	At/Post Delivery ^b
Informed Consent Process	X									
Medical History	X									
Obstetrical History	X									
Concomitant Treatment History	X	X	X	X	X	X	X	X	X	X
Rapid Diagnostic Test (eg, Binax)	X									
Complete Physical Exam	X									
Limited Physical Exam									X	
Oral Temperature	X	X	X	X	X	X	X	X	X	
Routine Obstetric checkup	X									
Ultrasound ^c	X									
Laboratory										
Peripheral Blood Smears ^d	X			X ^d	X ^d	X ^d	X ^d	X ^d	X ^d	
Hemoglobin (Hb)	X								X	
Urine Pregnancy Test ^e	X									
Urine Test for Glucose & Protein	X									
Blood Blot for Molecular Testing										
Molecular Genotyping for P. Falciparum ^f	X			X ^f	X ^f	X ^f	X ^f	X ^f	X ^f	
Genetic Marker for CQ Resistance	X									
Administer Treatment Azithromycin-Chloroquine (AZCQ ^g)	X	X	X							
Distribute Long lasting insecticidal-treated bednets (LLITs)	X									
Confirm the Installation of LLINs at Home by Fieldworkers		X								
Blood Samples for AZ, CQ and desethyl-CQ Analysis ^h	X ⁱ		X ^j	X ^k	X ^k	X ^k	X ^k			
Adverse Events Assessment	X	X	X	X	X	X	X	X	X	
Exposure in Utero (EIU) Assessment ^l										X

090177e1811d3ccb\Approved\Approved On: 19-Feb-2010 20:59

- ^a All tasks should be performed prior to the first dose except AE assessment and bednet distribution.

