5.5. Concomitant Medication(s)

The medications, not contra-indicated during pregnancy and not contra-indicated for co-administration with AZ or CQ, may be used through Day 42 following the first dose of AZCQ. After Day 42, the medications not contra-indicated during pregnancy may be used. All medications used by the subject at study entry or at any time through last study visit following the delivery or the termination of pregnancy must be recorded in the case report form. At each study visit, all medications taken since the last evaluation will be recorded.

While interactions with digoxin, ergot alkaloids, triazolam, carbamazepine, cyclosporine, hexobarbital and phenytoin have not been reported in clinical trials with AZ, they have been observed with macrolide products. Careful monitoring of subjects taking these medications is advised.

A single oral dose of AZ co-administered with nelfinavir at steady-state resulted in increased AZ serum concentrations. Although it is not necessary to adjust the dose of AZ when administered in combination with nelfinavir, close monitoring for known side effects of AZ (eg, liver enzyme abnormalities, hearing impairment) is warranted.

There have been reports which may indicate an increase in incidence and severity of adverse reactions when CQ is used with Fansidar as compared to the use of Fansidar alone (refer to Fansidar package insert).

Please refer to package inserts for AZ and CQ, and IB for AZCQ for further information regarding potential interactions between study drugs and other treatment agents

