6.1.6. Safety Follow-up Visit for EIU Assessment

Every attempt should be made to follow up the subject following delivery or at termination of pregnancy for EIU safety assessment. In case of no associated serious adverse events (SAE), subjects should be followed up by fieldworkers at clinic or at home within 14 calendar days after expected date of delivery or termination of pregnancy.

A. Following data will be collected at this visit:

- Concomitant treatment history;
- Maternal information and delivery: any history of complications during pregnancy, at and after delivery, eg, pre-eclampsia, hemorrhage, infection, etc;
- Neonatal Information (See Section 7.2 for details):
 - Outcome of pregnancy;
 - Outcome of infant.

When feasible and relevant for the assessment of the case (eg, in case of neonatal malformation/anomalies, premature delivery, low birth weight neonates, developmental assessment, kernicterus, or any other neonatal illness, hospitalization, drug therapy etc), further follow-up of neonates should continue until the information is satisfactory or the outcome has been established or the condition has stabilized.

B. In the event of an elective termination, spontaneous abortion, and late fetal death, following details should be recorded if available:

- Reason for termination;
- Gestational age at termination;
- Results of physical examination (gender, external anomalies) and pathology.

Any additional tests, procedures, treatments, and consultations may be conducted if recommended by local/national ANC guidelines and deemed clinically indicated by the investigator.

Any serious adverse events (SAEs) occurred after the informed consent through one month after the delivery or the termination of pregnancy should be reported to the study doctors immediately. Refer to Section 8.2 for details.

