7.2. Safety Assessments

Safety and tolerability will be assessed by spontaneously reported adverse events, history of concomitant treatments, temperature, hemoglobin concentrations, and EIU safety assessment according to Schedule of Activities.

- Spontaneous adverse events reporting: through Day 42. Refer to Section 8 (Adverse Event Reporting) for details;
- History of concomitant treatment assessment;
- Oral temperature through Day 42;
- Hemoglobin levels: with HemoCue™, via finger stick or peripheral blood collection) at baseline and on Day 42.
- EIU Assessments:

Every attempt should be made to follow up the subject after the delivery for EIU assessment. In case of no associated serious adverse events (SAE), subjects should be followed up by fieldworkers at clinic or at home within 14 calendar days after expected date of delivery or termination of pregnancy.

- Maternal information and delivery: any history of complications during pregnancy, at and after delivery, eg, pre-eclampsia, hemorrhage, infection, etc.
- Neonatal information:
 - Outcome of pregnancy:
 - Full term live birth;
 - Premature live birth;
 - Still birth;
 - Spontaneous abortion/miscarriage;
 - Induced or elective abortion;
 - Gestational age at birth.
 - Outcome of infant:
 - Normal neonate;
 - Congenital malformation/anomaly;
 - Other neonatal problem/abnormality: include dysmaturity, neonatal illness, hospitalization, drug therapies.

Infant details: include sex, weight at birth, length at birth, head circumference at birth, APGAR scores (1/5 minutes).

- Fetal information will be collected in the event of pregnancy termination.
- Additional information and further follow-up on the neonate will be conducted when feasible and relevant to the assessment of the case if applicable.

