8.2. Reporting Period

For serious adverse events, the reporting period to Pfizer or its designated representative begins from the time that the subject provides informed consent, which is obtained prior to the subject's participation in the study, ie, prior to undergoing any study-related procedure and/or receiving investigational product, **through Day 42 and including 39 calendar days after the last administration of the investigational product, or until one month after the delivery or the termination of pregnancy (which ever is later)**. If pregnancy outcome meets the classification as a serious adverse event, it will be reported accordingly as serious adverse event (refer to Section 8.9 for details). Any serious adverse event occurring any time after the reporting period must be promptly reported if a causal relationship to investigational product is suspected.

Adverse events (serious and non-serious) should be recorded on the CRF from the time the subject has taken at least one dose of study treatment through last subject visit.

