8.9. Exposure During Pregnancy

This is a study exclusively in pregnant women participants. Enrolled subjects will be asymptomatic pregnant women who will receive study drugs for preventive treatment of malaria. Since this is the first time AZ and CQ combination will be administered to pregnant women, all subjects will be followed up for EIU safety assessments following delivery or termination of pregnancy. The reason(s) for an induced abortion should be specified. All pregnancy-related AEs through Day 42 following the first dose of AZCQ and the pregnancy outcomes will be recorded on CRF pages as required clinical study data. Since all the information generally included on an EIU form will be collected on CRF paper, a separate EIU form is not required.

090177e1811d3ccb\Approved\Approved On: 19-Feb-2010 20:59

If the outcome of the pregnancy meets the criteria for immediate classification as a serious adverse event (ie, spontaneous abortion, stillbirth, neonatal death, or congenital anomaly [including that in an aborted fetus, stillbirth or neonatal death]), the investigator should follow the procedures for reporting serious adverse events.

In the case of a live birth, the “normality” of the newborn can be assessed at the time of birth (ie, no minimum follow-up period of a presumably normal infant is required before an Exposure in Utero Form can be completed). The “normality” of an aborted fetus can be assessed by gross visual inspection, unless pre-abortion test findings are suggestive of a congenital anomaly.

Additional information about pregnancy outcomes that are classified as serious adverse events follows:

- “Spontaneous abortion” includes miscarriage and missed abortion.
- All neonatal deaths that occur within 1 month of birth should be reported, without regard to causality, as serious adverse events. In addition, any infant death after 1 month that the investigator assesses as possibly related to the exposure during pregnancy to the investigational medication should be reported.

Additional information regarding the EIU may be requested by the investigator. Further follow-up of birth outcomes will be handled on a case-by-case basis (eg, follow-up on preterm infants to identify developmental delays). In the case of paternal exposure, the investigator must obtain permission from the subject’s partner in order to conduct any follow-up or collect any information.

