9.3. Safety Analysis

Adverse events, history of concomitant treatments, hemoglobin, temperature, and the EIU safety assessment will be recorded for each subject during the study according to the schedule of assessments. Standard safety reporting tables will summarize and list the safety data.

Each adverse event will be counted once according to the date of onset. If the adverse event onset was prior to the first dose of study drug and the event does not increase in severity after initiation of study drug, the adverse event is then considered to be a pre-treatment adverse event and will not be counted in the treatment-emergent adverse event incidence tables. If the onset is prior to the first dose of study drug and the severity increases thereafter, the event is counted as a treatment-emergent adverse event. An adverse event with onset after the first dose of study drug will be counted as a treatment-emergent adverse event. This rule is consistent with the treatment-emergent signs and symptoms (TESS) convention for counting adverse events.

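### Section 8.2 records adverse events to the post-delivery visit, Section 7.2 and the Schedule stop at Day 42, and Section 9.3 sets no end to treatment emergence, so the single-arm AE rates could cover unequal periods

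*Protocol*

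**What the plan says.** Four places in the protocol define how long adverse events are collected.

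- **Section 8.2**, on events both serious and non-serious: they "should be recorded on the CRF from the time the subject has taken at least one dose of study treatment through last subject visit".
- **Section 7.2**: "Spontaneous adverse events reporting: through Day 42".
- **Schedule of Activities**: the row "Adverse Events Assessment" is marked from Day 0 to Day 42. It has no mark in the At/Post Delivery column, where the EIU row does have one.
- **Section 8.9**: "All pregnancy-related AEs through Day 42 following the first dose of AZCQ and the pregnancy outcomes will be recorded on CRF pages". This limits pregnancy-related events only.

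Section 5.5 shows which visit is last. It requires concomitant medications "through last study visit following the delivery or the termination of pregnancy must be recorded in the case report form". Section 6.1.6 schedules that visit, absent an associated SAE, "within 14 calendar days after expected date of delivery or termination of pregnancy". The data listed for it are concomitant treatment, maternal complications ("any history of complications during pregnancy, at and after delivery"), and neonatal or fetal information. General AE assessment is not listed.

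For counting, Section 9.3 states: "An adverse event with onset after the first dose of study drug will be counted as a treatment-emergent adverse event". It gives no closing date.

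Section 8.2 also sets a separate SAE reporting period, from consent to the later of Day 42 or one month after delivery or termination. That rule is explicit and is not in dispute here.

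**The concern.** A site that follows 8.2 keeps recording non-serious events until after delivery. A site that follows 7.2 and the Schedule stops at Day 42. Nothing in the protocol says which instruction prevails, and the 9.3 rule would admit whatever was recorded to the treatment-emergent tables.

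Safety and tolerability of a 3-day course is a stated secondary objective, and Section 8.9 describes this as the first use of the combination in pregnant women. There is no control arm to show the background rate of pregnancy complaints, so the absolute incidence has to be readable by itself. It is readable only if the period it covers is defined. Under 8.2 and 9.3 taken literally, the period would depend on gestational age at entry. It would also run past Day 42, when subjects return to standard antenatal care that includes IPTp with SP where gestational age allows (Sections 3 and 4.4). An event after a later SP course would then count as treatment-emergent for AZCQ.

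**Working it through.** The protocol gives no figure of its own to reproduce. The check is a comparison of the passages and then date arithmetic.

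**Step 1: does the last subject visit mean Day 42?** It is hard to read it so. Section 5.5 ties the last study visit to delivery or termination. Section 8.2 itself writes Day 42 in its preceding paragraph when it means Day 42. The sentence also covers non-serious events explicitly, so it does not merely restate the SAE window. The conflict with 7.2 and the Schedule is real.

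**Step 2: length of the two windows.**

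Inputs:
- Gestational age at Day 0: 14 to 30 weeks (Section 4.1).
- Lag from delivery to the last visit, L: taken as 0 to 14 days (Section 6.1.6).
- Gestational age at delivery: **assumed** 40 weeks, with 37 and 42 weeks as the range. The protocol does not give it.

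Formula: days from Day 0 to last visit = 7 × (weeks at delivery − weeks at entry) + L.

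| Delivery (assumed) | Entry at 30 weeks | Entry at 14 weeks | Multiple of 42 days |
|---|---|---|---|
| 37 weeks | 49 to 63 days | 161 to 175 days | 1.2 to 4.2 |
| 40 weeks | 70 to 84 days | 182 to 196 days | 1.7 to 4.7 |
| 42 weeks | 84 to 98 days | 196 to 210 days | 2.0 to 5.0 |

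At 40 weeks the extremes are 7 × (40 − 30) = 70 days (10 weeks) and 7 × (40 − 14) + 14 = 196 days (28 weeks), against 42 days (6 weeks). Between two women with the same lag, the window differs by 182/70 = 2.6-fold (L = 0) or 196/84 = 2.3-fold (L = 14). Early termination of pregnancy would shorten the window further.

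**Step 3: how much of the window lies beyond Day 42?** At 40 weeks, from (70 − 42)/70 = 40% to (196 − 42)/196 = 79% of the calendar time.

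**Step 4: how is that time observed?** AE assessment is scheduled on Days 0, 1, 2, 7, 14, 21, 28, 35 and 42. None is scheduled after that, and the post-delivery visit does not list it. Later non-serious events would therefore be captured sparsely and unevenly. The multiples in Step 2 are calendar time. They are not ratios of AE rates.

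**The case against.** The strongest reply is that the problem can be repaired at analysis. Both readings collect events at the same visits through Day 42, and 9.3 counts events by onset date, so a Day 42 table could be cut from either data set. The end of a treatment-emergent window is also something an analysis plan commonly supplies, and Section 9 defers detailed methodology to one that is not shown. This largely stands: the missing end date in 9.3 would be no fault by itself. It matters because 8.2 feeds it with longer collection. A later cut-off could repair the table, but it could not tell sites which collection rule to follow.

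Second, Section 7.2 refers to Section 8 for details, so 8.2 might be meant to govern, and first use in pregnant women could justify wider collection. That is a fair argument for keeping the longer window. In that case the Schedule and Section 6.1.6 lack the AE assessment needed to carry it out.

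Third, a reader might take Section 8.9 as a general stop at Day 42. Its sentence limits only pregnancy-related events, so it supports the Day 42 reading in part.

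Fourth, a reader might infer that AE incidence would be inflated 1.7 to 4.7 times. The documents do not support that. The ratio is time elapsed under an assumed delivery date, and no AE elicitation is scheduled over the added weeks.

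**Conclusion.** The contradiction in the collection window stands, and the open-ended rule in 9.3 carries it into the safety tables. The consequence is conditional. If some or all sites follow 8.2 past Day 42 **and** no date cut is applied, the single-arm incidence would cover about 10 to 28 weeks of calendar time (7 to 30 weeks across the assumed delivery range of 37 to 42 weeks) in place of 6. The later part would be poorly ascertained and would include time after SP. If every site stops at Day 42, all women who complete that visit share one window and no mixing occurs. It would go too far to say that the AE rates will mix follow-up lengths.

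Nor does the contradiction by itself require non-serious collection to stop at Day 42. It requires one agreed window and a defined main table. The primary endpoint, its censoring rules and the sample size are unaffected, and with one arm there is no between-arm bias. This should be corrected because the safety result rests on absolute rates and the correction is cheap.

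**What to change.** 1. Reconcile Section 8.2 with Section 7.2 and the Schedule of Activities to one AE collection window, stated in the same terms in each place. If Day 42 is chosen, change the sentence in 8.2. If the post-delivery visit is chosen, change 7.2 and add AE assessment to that visit in the Schedule and Section 6.1.6. Align 8.9 for pregnancy-related events.
2. In Section 9.3, base the main treatment-emergent incidence tables on onset from first dose through Day 42.
3. Tabulate later-onset AEs (if collected), SAEs and pregnancy outcomes separately.
4. Leave the SAE window to one month after delivery or termination unchanged.

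The Day 42 option costs only wording; the longer option adds an AE assessment to a visit that already takes place. Either way, late non-serious events do not enter the main incidence table. If collection stops at Day 42, they would be seen only as far as the post-delivery history of complications records them, which is narrower than a general AE assessment. SAE and pregnancy-outcome data are retained in full.

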8.3. Definition of an Adverse Event

An adverse event is any untoward medical occurrence in a clinical investigation subject administered a product or medical device; the event need not necessarily have a causal relationship with the treatment or usage. Examples of adverse events include but are not limited to:

- Abnormal test findings;
- Clinically significant symptoms and signs;
- Changes in physical examination findings;
- Hypersensitivity;
- Progression/worsening of underlying disease.

Additionally, they may include the signs or symptoms resulting from:

- Drug overdose;
- Drug withdrawal;
- Drug abuse;
- Drug misuse;
- Drug interactions;
- Drug dependency;
- Extravasation.

8.4. Abnormal Test Findings

The criteria for determining whether an abnormal objective test finding should be reported as an adverse event are as follows:

- Test result is associated with accompanying symptoms; and/or
- Test result requires additional diagnostic testing or medical/surgical intervention; and/or

- Test result leads to a change in study dosing or discontinuation from the study, significant additional concomitant drug treatment, or other therapy; and/or
- Test result is considered to be an adverse event by the investigator or sponsor.

Merely repeating an abnormal test, in the absence of any of the above conditions, does not constitute an adverse event. Any abnormal test result that is determined to be an error does not require reporting as an adverse event.

8.5. Serious Adverse Events

A serious adverse event or serious adverse drug reaction is any untoward medical occurrence at any dose **for mothers or fetus** that:

- Results in death;
- Is life-threatening (immediate risk of death);
- Requires inpatient hospitalization or prolongation of existing hospitalization;
- Results in persistent or significant disability/incapacity;
- Results in congenital anomaly/birth defect.

Medical and scientific judgment should be exercised in determining whether an event is an important medical event. An important medical event may not be immediately life-threatening and/or result in death or hospitalization. However, if it is determined that the event may jeopardize the subject and/or may require intervention to prevent one of the other adverse event outcomes, the important medical event should be reported as serious.

Examples of such events are intensive treatment in an emergency room or at home for allergic bronchospasm; blood dyscrasias or convulsions that do not result in hospitalization; or development of drug dependency or drug abuse.

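### The SAE definition names mother and fetus but not the neonate, so non-fatal serious neonatal events are not clearly classed as SAEs

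*Protocol*

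**What the plan says.** Protocol Section 8.5 describes an SAE as "any untoward medical occurrence at any dose for mothers or fetus that" meets one of the listed criteria, so its scope is events "for mothers or fetus". One of these criteria is "Requires inpatient hospitalization or prolongation of existing hospitalization"; the others are death, threat to life, lasting disability and congenital anomaly. The important-medical-event clause in the same section asks whether "the event may jeopardize the subject and/or may require intervention to prevent one of the other adverse event outcomes".

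Section 8.2 keeps SAE reporting open "until one month after the delivery or the termination of pregnancy" when that is later than Day 42, and Section 6.1.6 repeats the one-month limit.

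Section 8.9 brings in certain pregnancy outcomes through a closed list: stillbirth, spontaneous abortion, congenital anomaly and neonatal death. It adds "All neonatal deaths that occur within 1 month of birth should be reported, without regard to causality, as serious adverse events". Infant deaths after one month are reportable if the investigator thinks them possibly related.

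Section 7.2 records non-fatal neonatal morbidity as an EIU outcome: "Other neonatal problem/abnormality: include dysmaturity, neonatal illness, hospitalization, drug therapies". Section 8.12.1 gives exposure-during-pregnancy cases the same 24-hour timeframe as SAEs.

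**The concern.** The phrase in Section 8.5 is specific to this study and names two of the three parties to a delivery. The third, the live-born infant, is exposed in utero and is followed for outcome. If a site applies Section 8.5 as written, a newborn's intensive-care admission is an EIU entry and not an SAE, while the same infant's death or malformation is an SAE.

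This matters because the EIU assessment is a named safety endpoint (Section 2.2), and Section 1.5.2.3.1 says that no well-controlled study has examined the co-administered drugs in pregnant women. SAE status also affects conduct: Sections 6.1.6 and 7.2 prescribe the fieldworker visit for subjects without an associated SAE. If sites read the definition differently, the SAE tables will reflect those readings as well as the events.

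**Working it through.** The point concerns a definition, so there is no plan figure to reproduce. The check is whether any provision makes a given event in a live-born infant an SAE.

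| Event in a live-born infant | Provision | Classed as SAE? |
|---|---|---|
| Death within one month | 8.9 | Yes |
| Congenital anomaly | 8.5, 8.9 | Yes |
| Death after one month, possibly related | 8.9 | Reportable |
| Non-fatal hospitalization | 7.2 (EIU item) | No provision found |
| Non-fatal life-threatening illness | 7.2 (EIU item, as neonatal illness) | No provision found |
| Disability without anomaly | None specific | No provision found |

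The clauses that might fill the last three rows are these:

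1. **Section 8.3** ties an adverse event to the trial subject who was given the product. That is the woman.
2. **Section 8.6** treats hospitalization as serious, but only for adverse events, so it leads back to Section 8.3.
3. **The important-medical-event clause in 8.5** protects the subject, again the woman.
4. **The list in Section 8.9** is introduced as exhaustive and contains no non-fatal neonatal morbidity.
5. **Section 8.12.1** sets a timeframe for exposure cases. Every pregnancy in this trial is an exposure case, and Section 8.9 waives the separate EIU form because the CRF carries the data. Neither section says which neonatal findings start the 24-hour clock.

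**Scheduled capture.** The EIU visit falls due no later than 14 days after the expected delivery date (Schedule of Activities, Section 6.1.6). Section 8.9 requires no minimum follow-up for an infant who appears normal. The Schedule of Activities shows adverse event assessment only through Day 42. Take a birth on the expected date and, as an assumption, a 30-day month. A visit on the last permitted day leaves 30 − 14 = 16 days of the SAE window with no scheduled assessment of the infant, and an earlier visit leaves more. An early birth can shrink or close this gap, because the visit is timed from the expected date. Section 6.1.6 does continue follow-up for a neonate with a known problem, where practicable and relevant. It does not help with an infant who is well at the visit and is admitted later.

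**The case against.** The strongest reply is that the protocol can be read as covering the infant already. A fetus cannot be admitted to hospital in its own right, so applying the hospitalization criterion to mothers and fetus suggests that fetus was meant loosely as offspring. Section 6.1.6 sets out neonatal data and then, in the same section, asks for any SAE through one month after delivery. This reading is reasonable, but Section 8.3 and the closed list in Section 8.9 point the other way. What stands is that the wording is ambiguous and that sites may differ.

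Three stronger readings are tempting, and the documents do not support them:

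- A reader might infer that serious neonatal illness never triggers a 24-hour report. Section 8.12.1 gives exposure-during-pregnancy cases that timeframe independently of SAE status. What is missing is a stated trigger.
- A reader might infer that these events reach the sponsor or the IDMC only through the routine EIU record, or are lost. Sections 6.1.6 and 7.2 collect and follow neonatal illness and hospitalization, and Section 9.3 includes the EIU assessment in the safety summaries and listings. Section 9.6 does not limit the IDMC's review to SAEs and leaves its guidelines to a charter that is not at hand.
- A reader might infer that the one-month window in Section 8.2 contradicts Section 8.5. It does not, because the window has a full use for maternal SAEs after delivery and for neonatal deaths. The neonate's absence from Section 8.5 is an omission.

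**Conclusion.** The point holds as a gap in classification. Taken literally, Sections 8.3, 8.5 and 8.9 leave non-fatal hospitalization, life-threatening illness and disability in a neonate outside the SAE definition during a period when SAE reporting is open. Such events are still recorded when known at the EIU visit. What is missing is SAE status, a clear trigger for the 24-hour timeframe, and scheduled capture of an admission between the EIU visit and the end of the month.

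The severity is low. No efficacy estimate, sample size or planned data item changes. I give no expected number of affected infants: the documents contain no rate of neonatal admission or serious illness, and any count would only restate an assumed rate. The conclusion rests on reading fetus in its ordinary sense. If offspring was intended, the remedy is the same and serves as clarification.

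**What to change.** - In Section 8.5, change the scope to: *for mothers, fetus or neonate (through one month after birth)*.
- In Section 8.9, add that a neonatal event meeting any Section 8.5 criterion is reported as an SAE, beside the deaths and anomalies already listed.
- Align Section 8.3, so that an event in the neonate can count as an adverse event for this purpose.
- Align Section 8.12.1, so that it says which neonatal events start the 24-hour timeframe.

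The cost is a few words in these sections and some additional SAE forms. No visit, procedure or analysis is added.
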